Several score systems have been proposed in order to intraoperatively stratify patients based on their risk of developing POPF, allowing a risk-adjusted approach to the reconstructive phase of PD.^{1,2} The fistula risk score (FRS) is the most used and extensively validated, and it is based on predictors such as pancreatic parenchyma texture, presumed pathology, main pancreatic duct diameter and estimated intraoperative blood loss (EBL). This prognostic score is able to identify a high-risk cohort (FRS 7-10) representing about 10% of all PDs and having an increased rate of POPF (around 30% and up to 40% in the FRS 10 patients) and consequently worse postoperative outcomes with a major postoperative morbidity around 35%.^{3,4} Recently, a large multi-institutional retrospective study and a randomized controlled trial both identified an optimal combination of therapeutic strategies able to mitigate the incidence and the burden of POPF in high-risk patients. Those “mitigation strategies” were the use of externalized trans-anastomotic stent (ETS), pancreatico-jejunal anastomosis (PJ), drains placement and the omission of prophylactic octreotide.^{4,5} However, both morbidity and mortality rates after high-risk PD (HR-PD) remain extremely high, even after the implementation of the above-mentioned strategies.⁵ Due to its clinical burden, POPF is still associated with delays (> 8 weeks) or omission of adjuvant therapy in two-thirds of complication-bearing patient.⁴

Given the increased postoperative burden of high-risk PDs, total pancreatectomy (TP) might be advocated for those who are at a high-risk for POPF, especially after recent studies showing improved postoperative outcomes of TP at high-volume centers. Stoop et al. found that the historic major postoperative morbidity of 34% after TP decreases to 23% when considering only the most recent years, similarly to another bicentric study including patients undergoing TP from 2000 to 2014.^{6,7} A more recent multicenter snapshot study, including TP performed at both high- and low- volume centers between 2018 and 2019, showed a major morbidity of 25% and an in-hospital mortality of 5%.⁸ Moreover, recent studies have reported improved postoperative quality of life (QoL) after TP compared to the past, presumably due to centralization at high-volume centers and development of long-acting insulin and modern pancreatic enzyme preparations.^{6,9,10,7}

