Given the encouraging postoperative outcomes after TPs at high-volume centers, we conducted a retrospective analysis of all PDs and TPs performed at the Verona Pancreas Institute from July 2017 to December 2019 to evaluate TP as an alternative to PD in patients at high risk for POPF development.¹¹ Albeit the extensive application of the currently recognized mitigation strategies in the HR-PD group, including the use of externalized pancreatic stent and jejunostomy, patients who underwent TP exhibited comparable mortality (3% vs 4%, $p=0,6$) and strikingly better postoperative outcomes. In the HR-PD group, the rates of abdominal fluid collection, PPH, DGE, and LOS were nearly doubled, and the rate of sepsis was three times higher than those in the TP group. Major morbidity defined as Clavien-Dindo ≥ 3 was 1,5-fold higher in the HR-PD group (19% vs 31%; $p=0,05$). Additionally, cancer- and pancreas- specific QoL seemed to be comparable, while endocrine insufficiency and insulin-dependent diabetes occurred in the totality of patients after TP and TP was associated with worse diabetes-specific QoL. Furthermore, we identified a small cohort of patients (FRS 9-10) at extremely high-risk for POPF (60%) and major morbidity (55%).

This retrospective analysis suggests a role for TP after PD in selected patients at extremely high-risk for POPF after adequate counselling. For the sake of making progress in the management of the pancreatic remnant in high-risk scenario, we firmly believe that these findings need to be confirmed in a randomized fashion.

AIM OF THE STUDY

In patients at extremely high risk for POPF and related severe complications, TP may represent a potential rescue strategy to avoid the morbidity related to the pancreatic anastomosis.

The aim of the present study is to compare TP and primary pancreatic anastomosis (PA) in a cohort of extremely high-risk patients.

OBJECTIVES

PRIMARY OBJECTIVE

To evaluate whether TP is superior to PA in reducing major morbidity, defined as Clavien-Dindo ≥ 3 , in patients with extremely high-risk pancreas.

SECONDARY OBJECTIVES

- To evaluate the incidence and severity of general and pancreas-specific (POPF, postoperative pancreatitis, DGE, PPH, sepsis) postoperative complications and mortality in each group
- To evaluate time to functional recovery and length of hospital stay (days) in each group
- To evaluate the incidence and severity of postoperative endocrine and exocrine insufficiency in each group

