- Respiratory distress (defined as the need for mechanic ventilation after surgery)
- Urinary tract infection
- Neurological morbidity (cerebrovascular accidents, hemorrhage)
- Re-operation
- Re-admission within 30, 60 and 90 days

For PA Group additional secondary endpoints are:

- Incidence and severity of POPF ²⁸
- Incidence of biochemical leak ²⁸
- Overall average complication burden for POPF
- Incidence of postoperative pancreatitis ²⁹

SAMPLE SIZE CALCULATION

A recent metanalysis by Schuh et al. reported a POPF rate around 23% in stage D patients (main pancreatic duct diameter ≤ 3 mm, soft pancreas) but no data were available regarding major morbidity¹². Patients that will be considered eligible for the present trial will have further features increasing their risk of POPF and

related major morbidity, compared to stage D patients. Based on the current literature and on a recent retrospective study by the Verona group, considering only a cohort of patients with extremely high FRS (FRS 9-10), the rate of major morbidity can be estimated around 55% after PD and 19% after TP.¹¹

The original risk score proposed in this trial is extrapolated based on previous literature and expert opinions. For this reason, there are no data directly available for estimation of major morbidity in this rare subset of patients, for which we estimate a rate of Clavien-Dindo ≥ 3 of around 40%.

Considering a 1:1 allocation between the groups, a sample size of 49 patients per group would allow a two-sided, two-sample test for binomial proportions to detect a difference in Clavien-Dindo ≥ 3 of 25% (40% vs 15%) with 80% power ($1-\beta$) and an error α of 0,05. The study has a group sequential design allowing for interim analyses at pre-specified timepoints with possible early stopping for efficacy or futility in case of an overwhelming large or small effect, respectively. Considering that extremely high-risk cases represent around 7% of the total amount of PDs performed and that the fistula risk can only be assessed intraoperatively, we expect to approach preoperatively around 1300 patients.

STATISTICAL ANALYSIS

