Continuous variables will be expressed as the means and standard deviation values or as median values with ranges and will be compared using the Student t-test or the Mann-Whitney test as appropriate. Categorical variables will be analyzed by Chi-square or Fisher's exact test in case of expected small frequencies. All the tests will be 2-tailed. P values < 0.05 will be considered statistically significant. All endpoints will require the above-mentioned statistical analysis, comparing the two study arms. Statistical analyses will be performed using STATA14 for Windows.

DURATION AND END OF THE STUDY

Since the Department of General and Pancreatic Surgery performs about 250 PD per year and the study will be proposed to at least other 2 international referral centers, the primary endpoint will be reached after 25 months: 22 months of patients' enrollment and 3 months of follow-up. Long term analysis of QoL and pancreatic insufficiency will require additional 24 month of follow-up. Time for data analysis must be considered negligible. All the patients undergoing PD will be enrolled for the study if inclusion and exclusion criteria will be respected. The study will be discontinued in case of reaching the statistical significance of the primary endpoint, or in case of suspension by the coordinators or by the authorities.

PROCEDURES RELATED TO REGISTRATION AND DATA MANAGEMENT

To ensure the confidentiality of data, each patient will be registered and de-identified by an identification code.

Each subject will be identified by a code consisting of:

- Code Protocol: TETRIS
- Number of the institution: (e.g. Patient recruited at the Verona Pancreas Institute will be coded as TETRIS_C1)
- Number of recruitment (e.g. the third patient recruited at the Verona Pancreas Institute will be coded as TETRIS_C1_3).

The P.I. of the study will be responsible for data protection and privacy of study participants by treating the data solely for statistical purposes and scientific research, and he will not communicate them if not anonymously. The manager of data processing is the principal investigator.

All data of enrolled patients collected during the study will be recorded in a computerized case report form (CRF) and transferred automatically into a specific database protected by passwords. These data will be kept confidential and will be treated in full compliance with the Legislative Decree 196/03.

ETHICAL CONSIDERATIONS

[figure not shown]

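### The sizing uses an unsourced 15% major morbidity rate after TP, below every TP rate the protocol cites; at its own 19%, with PA kept at 40%, power is about 63%

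*Combined protocol and SAP*

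**What the plan says.** The section SAMPLE SIZE CALCULATION (combined protocol and SAP) refers to the centre's retrospective study and to patients with FRS 9-10, and says that "the rate of major morbidity can be estimated around 55% after PD and 19% after TP". It then explains that the trial's risk criteria are new and that no direct data exist for this population, and puts the major morbidity rate at about 40%. The design statement follows: "a sample size of 49 patients per group would allow a two-sided, two-sample test for binomial proportions" to detect a difference "of 25% (40% vs 15%) with 80% power" "and an error α of 0,05". No reason or source is given for the 15%.

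The background, before AIM OF THE STUDY, reports the same retrospective study differently. Major morbidity was "1,5-fold higher in the HR-PD group (19% vs 31" per cent), a comparison of the whole TP group (19%) with the whole high-risk PD group (31%). The FRS 9-10 cohort is described afterwards, with 55% major morbidity and no TP figure.

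The background also cites other TP series. One fell from 34% historically to 23% in recent years. A multicentre snapshot "showed a major morbidity of 25% and an in-hospital mortality of 5" per cent.

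**The concern.** The section gives two different TP rates, 19% as the estimate and 15% as the design input, and does not connect them. The move from 55% to 40% for PA is at least explained, by the new criteria and the lack of data. The move from 19% to 15% for TP is not explained, and it takes the rate below all the TP evidence cited.

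Separately, pairing 55% with 19% under an FRS 9-10 label suggests a 36-point contrast (55 − 19) within one cohort. On the background text, the two figures come from different comparisons.

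At stake is how far the stated 80% can be relied on. If TP morbidity is what the centre's own study found and PA morbidity is what the protocol assumes, the chance of missing a real effect is about 37%, not about 20%. Someone reading only the sizing section would not learn this.

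**Working it through.** **Inputs.** All are from SAMPLE SIZE CALCULATION unless noted: n = 49 per arm; allocation 1:1 ("Considering a 1:1 allocation between the groups"); α = 0.05; two-sided (STATISTICAL ANALYSIS: "All the tests will be 2-tailed"); design rates 40% (PA) and 15% (TP). Alternative TP rates are 19% (same section and background), and 23%, 25% and 34% (background). The planned test is chi-square, with Fisher's exact for small expected counts. At the design rates the smaller expected count is 49 × 0.275 = 13.5 per arm, so chi-square is the relevant test.

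**Step 1: reproduce the plan's figure.** Pooled normal approximation, with p̄ = (p₁ + p₂)/2:

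n = [1.960·√(2p̄(1−p̄)) + 0.842·√(p₁(1−p₁) + p₂(1−p₂))]² / (p₁ − p₂)²

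For 0.40 and 0.15, p̄ = 0.275 and n = (1.238 + 0.510)² / 0.25² = 48.9, rounded up to 49. The stated sample size is reproduced.

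**Step 2: power with n fixed at 49.**

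Power = Φ{ [|p₁ − p₂|·√49 − 1.960·√(2p̄(1−p̄))] / √(p₁(1−p₁) + p₂(1−p₂)) }

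- 40% vs 15%: (1.750 − 1.238)/0.606 = 0.845, so power is 80.1%.
- 40% vs 19%: (1.470 − 1.264)/0.628 = 0.328, so power is 62.9%.

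**Step 3: the other rates, with exact binomial enumeration of the uncorrected chi-square test as a check.**

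| PA | TP | Power, approximation | Power, exact | n per arm for 80% (approximation) |
|---|---|---|---|---|
| 40% | 15% | 80.1% | 80.9% | 49 |
| 40% | 19% | 62.9% | 63.3% | 73 |
| 40% | 23% | 44.0% | 43.9% | 117 |
| 40% | 25% | 35.2% | 34.9% | 152 |
| 40% | 34% | 8.9% | 9.2% | 1016 |
| 55% | 19% | 96.9% | 96.7% | 28 |

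With Fisher's exact test, power would be 74.6% at 40% vs 15% and 55.3% at 40% vs 19%. No figure here allows for interim analyses or losses.

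**Step 4: the attribution.** The two accounts of the retrospective study, side by side:

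| Group | Background | Sample size section |
|---|---|---|
| All TP | 19% | not mentioned |
| All high-risk PD | 31% | not mentioned |
| FRS 9-10, PD | 55% | 55% |
| FRS 9-10, TP | no figure | 19%, as the sentence is written |

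The last row is the mismatch. It does not affect the 49, because 19% is not used in the calculation.

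**The case against.** The arithmetic is right, and a reader might infer from the 63% that the sample size was miscalculated or that the trial's true power is 63%. Neither follows. The 63% changes one input and holds PA at 40%. With the pair printed in the sizing section, 55% vs 19%, power would be 97%. That point stands and belongs in any fair sensitivity range, but 97% is not the design power either, because the protocol itself replaces 55% with 40%.

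A reader might also infer that the protocol's evidence contradicts a 25-point difference. It does not: the documents give 12 points (31 − 19) across all high-risk patients and 36 points (55 − 19) if FRS 9-10 PD is set against overall TP, and 25 lies between them. What lacks support is the TP level of 15%.

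Nor does 19% refute 15%. The documents do not give the size of the TP group. If it were between 50 and 150 patients (an assumption), the 95% half-width, 1.96·√(0.19 × 0.81/n), would be about 11 to 6 points, so 15% would lie within the interval. The other comparators also differ in weight: 34% is described as historic, and the 25% series includes low-volume centres while this trial plans referral centres. These points make 19% the most relevant comparator, and it is still above 15%.

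The 25 points could be a target difference rather than an expectation, but the document does not say so, and the section argues from observed rates. Finally, the FRS 9-10 phrase may have been meant to qualify only the PD figure. The cited study is not available to settle that; as written, the phrase covers both.

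**Conclusion.** The concern holds as an unsupported design input and an unclear attribution, not as an error of calculation. The 49 per arm and 80% power are correct for 40% vs 15%. The 15% is unsourced, 4 points below the TP estimate in the same section, and below every TP rate cited.

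If TP is 19% and PA is 40%, power with 98 patients is about 63%. Over the cited recent TP rates of 19% to 25%, it falls from 63% to 35%. These figures assume a two-sided uncorrected chi-square test at 0.05, 49 evaluable patients per arm and a single analysis. They depend on PA staying at 40%, which is the sponsor's own estimate without direct data.

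A reader might go further and conclude that the trial must be enlarged to 146 patients (2 × 73). The documents do not support that as a requirement, since the PA rate is as uncertain as the TP rate and a higher PA rate would restore the power. The claim that can be defended is that the stated 80% applies to one alternative, whose TP rate the protocol does not justify.

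**What to change.** In SAMPLE SIZE CALCULATION:

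1. Correct the attribution: 19% is the overall TP group, set against 31% in all high-risk PD; 55% is PD with FRS 9-10, for which no TP rate is reported. If the source study does contain a TP rate for FRS 9-10, report that instead.
2. State the basis for 15% (for example, that 25 points is a target difference, if that was the intention), or replace it with the documented 19%.
3. Restate power for the planned 98 patients by the exact chi-square calculation: 81% for 40% vs 15% and 63% for 40% vs 19%. Add the rest of the TP range (44% at 23%, 35% at 25%), label the 40% PA rate as an assumption, and give 55% vs 19% (97%) as the favourable extreme.

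The cost is a change of protocol wording. Enrolment, procedures and analysis need not change. The downside is that the stated power becomes less favourable.

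### The 5% error rate and 80% power come from a single-look test, but the trial is group sequential and its only written stopping threshold is an unadjusted p < 0.05

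*Combined protocol and SAP*

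**What the plan says.** Under Sample Size Calculation the protocol assumes equal allocation and states that "a sample size of 49 patients per group would allow a two-sided, two-sample test for binomial proportions". The target is major morbidity of 40% in one group against 15% in the other, at 80% power and alpha 0.05. The next sentence changes the design: "The study has a group sequential design allowing for interim analyses at pre-specified timepoints with possible early stopping for efficacy or futility". That sentence goes on to reserve early stopping for effects that are very clearly large or very clearly small. It gives no number.

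Two later places bear on how a stop would be decided. Under Statistical Analysis: "P values < 0.05 will be considered statistically significant". This applies to all tests, with no separate level for interim or final analyses. Under Duration and End of the Study: "The study will be discontinued in case of reaching the statistical significance of the primary endpoint".

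Nowhere do the documents give the number or timing of looks, an efficacy boundary or spending function, a futility rule, whether futility is binding, or a final critical value.

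**The concern.** The alpha and the power in the sample size section belong to a trial analysed once. A trial that may stop at interim looks has its own type I error and power, and both depend on the boundaries. The only boundary a reader can find is 0.05, linked to a rule that ends the study on significance. Repeated use of that level gives more chances of a false-positive result.

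This matters for a comparison of total pancreatectomy (TP) with PA. The protocol's background reports insulin-dependent diabetes in all patients after TP, so a false claim that TP reduces major morbidity would be costly. If stricter bounds are intended, the open question becomes how much of the 80% power remains.

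**Working it through.** **Inputs.** From Sample Size Calculation: 49 per group, 40% vs 15%, two-sided alpha 0.05, 80% power, 1:1 allocation. From Statistical Analysis: chi-square test, or Fisher's exact test when expected frequencies are small; significance at p < 0.05. Looks and boundaries are not in the documents. I assumed equally spaced looks at 25/49, 16/33/49 and 10/20/29/39/49 patients per group.

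**1. The plan's own figure.** Single look, pooled variance, mean rate 0.275:

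n = [1.96·√(2·0.275·0.725) + 0.8416·√(0.40·0.60 + 0.15·0.85)]² / 0.25²
= [1.2377 + 0.5102]² / 0.0625 = 48.88, rounded up to 49.

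The stated number is therefore exactly the one-look number, with nothing added for interim analyses. Exact chi-square power at 49 per group is 80.9%.

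**2. Type I error if p < 0.05 is applied at every look.** I enumerated all binomial outcomes exactly with a common event rate of 27.5%, stopping for significance only.

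- 1 look: 5.0%
- 2 looks: 5.4% at the first + 3.2% at the second = 8.6%
- 3 looks: 5.8% + 3.5% + 2.3% = 11.6%
- 5 looks: 13.5%

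Normal theory gives 8.3%, 10.7% and 14.2% for 2, 3 and 5 looks. If Fisher's test replaces chi-square wherever an expected count is below 5 (my reading of small), the exact figures are 8.5%, 9.6% and 11.7%. Under 40% vs 15%, this unadjusted rule raises power, to 83.1%, 84.5% and 85.5%.

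**3. Power at 49 per group if alpha is preserved.** Two-sided bounds with overall alpha 0.05 are: O'Brien-Fleming Z = 2.797, 1.977 (2 looks) and 3.471, 2.454, 2.004 (3 looks); Pocock Z = 2.178 (2 looks) and 2.289 (3 looks). Z > 0 favours TP. The current-trend futility rule stops when conditional power is below 20%, that is, when Z < √t·(c − 0.8416·√(1−t)), where t is the information fraction and c the final critical value. For O'Brien-Fleming at 25/49 this is 0.714·(1.977 − 0.8416·0.700) = 0.99.

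| Rule (futility binding) | 2 looks | 3 looks |
|---|---|---|
| O'Brien-Fleming, efficacy only | 81.0% | 80.4% |
| O'Brien-Fleming, futility if Z < 0 | 80.9% | 79.5% |
| O'Brien-Fleming, conditional power < 20% under the design effect | 80.6% | 79.9% |
| Pocock, efficacy only | 76.6% | 73.8% |
| O'Brien-Fleming, conditional power < 20% under the current trend | 75.3% | 70.8% |
| Pocock, conditional power < 20% under the current trend | 71.1% | 61.6% |

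**4. A design that restores both figures.** One look at about 24–25 per group, two-sided p < 0.005 at interim (Z = 2.807) and p < 0.048 at the end (Z = 1.977), with futility if Z < 0. Power is 80.9%. Type I error at a common rate of 27.5% is 5.1% without counting the futility stop, which can only lower it.

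**The case against.** The best defence has three parts.

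First, the stated sample size can stand. Standard O'Brien-Fleming bounds with no or mild futility stopping keep power at about 80–81% with 98 patients. The protocol's remark that stopping is for overwhelming effects points to this end of the range and away from Pocock bounds or an aggressive futility rule. This stands. A reader might infer that the trial is underpowered, or that futility stopping is bound to take most of the loss. The documents support neither: the large falls in power all need rules that the protocol does not state.

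Second, the protocol does not say that p < 0.05 applies at each interim look. It calls the timepoints pre-specified, and a stricter bound may have been intended. This also stands as a limit on the claim: the inflated error rates are what follows if the written threshold is used at the looks. They are not a demonstrated property of the trial.

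Third, one could call this mere missing detail. That does not stand. A level is written down, and so is a rule that ends the study on reaching significance. Taken together they do not give the 5% in the sample size section, and nothing else in the documents overrides them. The remark about overwhelming effects is not a boundary that anyone could apply.

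**Conclusion.** The concern holds as one about undetermined operating characteristics, with type I error first. The 49 per group is a correct single-look calculation attached to a group sequential trial. Under the only threshold written, two-sided type I error is about 8.6%, 11.6% and 13.5% for 2, 3 and 5 looks, against a stated 5%. Under alpha-preserving bounds with 2 or 3 looks, power runs from about 81% down to about 62%, and the protocol's wording favours the upper end.

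These figures rest on equally spaced looks, a common event rate of 27.5% for the error rates, uncorrected chi-square tests and binding futility. Using Fisher's test at small early looks lowers the 3- and 5-look error rates by about 2 points but does not bring them near 5%. It would be wrong to conclude that 98 patients are too few. The plan should be corrected, but the sample size need not change.

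**What to change.** Before any interim data are seen, amend Sample Size Calculation, Statistical Analysis, and Duration and End of the Study so that they describe one design:

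- State the number and timing of looks, the efficacy bounds, the futility rule and whether it is binding, and the final critical value.
- Replace discontinuation at p < 0.05 with those bounds, and exempt the primary endpoint from the general 0.05 level.
- Report the power of that design.

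One workable version is a single interim look once about 49 patients have a known primary outcome, with O'Brien-Fleming bounds (two-sided p < 0.005 at interim, p < 0.048 at the end) and futility only if the interim difference favours PA (Z < 0). Power is about 80–81% at 98 patients. If more looks, Pocock-type bounds or a more aggressive futility rule are preferred, state the lower power or recalculate the sample size. For efficacy stopping only, 80% power with Pocock bounds needs about 55 (2 looks) or 58 (3 looks) per group.

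The cost is protocol wording and a short calculation. No patients are added. The final threshold becomes slightly stricter (0.048 instead of 0.05), and a trial stopped under the Z < 0 rule gives up the chance to show at the final analysis that PA is better.

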- Absence of at least one minor criteria
- Absence of interobserver agreement between at least 2 surgeons
- More than 1 extension of resection to pancreatic neck due to pancreatic margin positivity

Postoperative

- Wrong randomization

Procedures

Preoperative care

Preoperative care will follow institutional standards, according to each center involved. After obtaining the informed consent for elective pancreatic resection and after adequate counselling, the study will be proposed to the patient. Patients with a main pancreatic duct of the pancreatic neck/body >3mm at preoperative imaging (CT scan or MRI) will be excluded. If the patient will accept, the informed consent will be obtained. The physician who will get the informed consent for the procedure will also be responsible for the consent

to the study. Randomization lists will be provided for each Center and for each randomized group. All patients will be preoperatively checked for diabetes by measuring fasting blood glucose (FBG) and Hb1Ac, C- peptide, and for pancreatic exocrine insufficiency by associated clinical criteria and fecal elastase-1 (FE-1) determination.

Intraoperative setting

The resection phase will be carried out according to clinical practice at each participating center. At the time of pancreatic anastomotic reconstruction, the risk will be calculated on the basis of the presence of major and minor criteria (see Table 1):

- The operating surgeon will assess pancreatic texture by manual palpation (only the distinction between “hard” and “soft” is allowed; the expert pancreatic surgeon manual palpation represents the gold standard for pancreatic texture assessment)¹³
- The operating surgeon will precisely measure the main pancreatic duct caliber in millimeters
- The operating surgeon will assess other risk features related to the pancreatic remnant such as: presence of bleeding, friable or deep pancreatic stump¹⁴; presence of invisible, eccentric or posterior main pancreatic duct; presence of intraoperative pancreatitis; FRS 9 or 10¹
- The operating surgeon will confirm the presumed pathology and estimated blood losses will be assessed in order to calculate the FRS

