each Institution's standards of care. In the PJ Group, the amylase value of drain fluids will be checked on POD1, POD3 and at any POD if it will help to diagnose a still undiscovered POPF. Surgical drain will be managed according to clinical judgment and each Institution's clinical standards. During hospitalization, all patients will receive specialistic evaluation to assess and possibly treat the occurrence of new onset diabetes or the worsening of pre-existing diabetes. Pancreatic exocrine insufficiency will be treated with oral supplementation of pancreatic enzymes if needed. Patients in the TP Group will be vaccinated 1 month after complete functional recovery against Pneumococcus, Hemophilus influenzae group B, and Meningococcus to minimize the likelihood of developing post-splenectomy sepsis. All patients will receive an outpatient follow-up, 1 month after discharge and every 6 months for 2 years. During follow-up, glycemic control, nutritional status, and possible symptoms of exocrine insufficiency will be assessed, and patients will receive specialistic assistance if needed. QoL will be registered using specific questionnaires. An oncologic evaluation will determine the indication for administration of adjuvant therapy, in case of malignancy.

Questionnaires

All patients who will be alive after at least 12 months of follow-up will be enrolled in the cross-sectional study of quality of life. All the eligible patients who are not able to attend outpatient visits will be contacted by telephone before receiving the 5 questionnaires by mail. Patients who will not respond within 1 month will be contacted again by telephone. Four questionnaires will be administered: (1) the EuroQoL Group questionnaire (EQ-5D); (2) the European Organization for Research and Treatment of Cancer (EORTC) QLQ-C30 questionnaire; (3) the European Organization for Research and Treatment of Cancer (EORTC) QLQ-PAN26 questionnaire; and (4) the Problem Areas in Diabetes (PAID) questionnaire.^{17 18 19 20} The comprehensive assessment will consist of a total of 116 questions.

ENDPOINTS

Primary endpoint

For each study group the primary endpoint is the rate of postoperative major morbidity, defined as Clavien-Dindo ≥ 3 .

Secondary endpoints

For each study group secondary endpoints are:

- Incidence of In-hospital, 30-days and 90-days postoperative mortality. Beyond these time-limits, the mortality that may be related to the operation will be considered and discussed in each case.

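### The primary test ignores centre and the pre-randomisation fistula risk score: valid, but a modest gain in efficiency is left unused

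*Combined protocol and SAP*

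**What the plan says.** The primary endpoint is binary: "the primary endpoint is the rate of postoperative major morbidity, defined as Clavien-Dindo ≥ 3". Under Statistical Analysis, "Categorical variables will be analyzed by Chi-square or" Fisher's exact test where expected counts are small. The section then adds: "All endpoints will require the above-mentioned statistical analysis, comparing the two study arms". No covariate, stratum or centre term is named for any endpoint.

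Three other places bear on this:

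- **Preoperative care** says that randomisation lists are supplied per centre. It also says per randomised group, which is not explained. FRS is not named as a stratification factor.
- **Intraoperative setting** has the score worked out during the eligibility assessment: "The operating surgeon will confirm the presumed pathology and estimated blood losses will be assessed in order to calculate the FRS". Randomisation follows that assessment. Material and Methods says that intraoperative data are recorded prospectively.
- **Sample Size Calculation** is also unadjusted: "a sample size of 49 patients per group would allow a two-sided, two-sample test for binomial proportions", for 40% against 15%.

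On prognosis, the background gives major morbidity of about 35% for FRS 7-10 and 31% for the sponsor's own high-risk PD group, with a small FRS 9-10 subgroup at 55%. All of these are rates after PD.

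**The concern.** A baseline variable that is already collected, is known before allocation and is related to the endpoint can be used at almost no cost, and FRS appears to be one. It still varies after selection. FRS 9-10 is only one of seven minor criteria in Table 1, any one of which suffices. The sponsor also plans on 40% in the anastomosis arm and not on the 55% seen at FRS 9-10, which implies a mixed population.

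Centre is a second unused variable. If allocation is balanced within centre, the analysis should reflect it. Anastomotic technique and mitigation strategies are left to each centre, so risk could plausibly differ between centres.

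At stake is some power in a trial with little to spare. The planned number gives almost exactly 80% power with no stated dropout allowance. Eligible cases are about 7% of PDs, and about 1300 patients must be approached. If nothing is pre-specified, any later adjustment prompted by a visible imbalance would be post hoc.

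**Working it through.** **1. The plan's own figure.** Take 40% vs 15%, two-sided α 0.05, 80% power, 1:1, pooled variance and no continuity correction. The mean rate is 0.275.

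n = [1.960·√(2·0.275·0.725) + 0.842·√(0.24 + 0.1275)]² / 0.25² = (1.238 + 0.510)² / 0.0625 ≈ 48.9, so 49 per arm. Power at 49 is 80.1%. The stated figure reproduces.

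**2. Inputs for the adjusted analysis.** From the documents: 55% after PD at FRS 9-10, 40% overall in the anastomosis (PA) arm, 15% overall in the total pancreatectomy (TP) arm, 49 per arm. Assumed, because the documents do not give them: the share f at FRS 9-10 (0.1 to 0.6), and the FRS effect after TP (either none, or the same odds ratio as in PA).

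**3. Formulas.**
- PA rate below FRS 9: lo = (0.40 − 0.55f)/(1 − f). Gap in PA: g = 0.55 − lo. The gap in TP is h (0 if there is no effect).
- Crude variance (per patient per arm): 0.24 + 0.1275 = 0.3675.
- Adjusted variance: 0.3675 − f(1−f)(g² + h²) + f(1−f)(g − h)²/2.
- SD of the between-arm difference in the FRS 9-10 share: √(2f(1−f)/49).
- Shift in the crude difference at one SD: SD × (g + h)/2.

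Example, f = 0.5 and no TP effect: lo = 0.25, g = 0.30, f(1−f)g² = 0.0225. Adjusted variance = 0.3675 − 0.0225 + 0.01125 = 0.35625, a fall of 3.1%. SD = 0.101; shift = 0.101 × 0.15 = 1.5 points.

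**4. Results, FRS only.** Power is from 200,000 simulated trials per scenario: crude chi-square, then Mantel-Haenszel on two FRS strata.

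| f | lo | FRS effect after TP | Variance saved | Power, crude → stratified | Shift at 1 SD (points) |
|---|---|---|---|---|---|
| 0.1 | 0.383 | none | 0.3% | 80.8 → 80.1% | 0.5 |
| 0.1 | 0.383 | same OR | 0.9% | 81.0 → 80.9% | 0.8 |
| 0.3 | 0.336 | none | 1.3% | 81.0 → 80.7% | 1.0 |
| 0.3 | 0.336 | same OR | 3.2% | 81.0 → 81.7% | 1.6 |
| 0.5 | 0.250 | none | 3.1% | 80.9 → 81.5% | 1.5 |
| 0.5 | 0.250 | same OR | 7.0% | 80.9 → 83.3% | 2.3 |
| 0.6 | 0.175 | none | 4.6% | 80.8 → 82.1% | 1.9 |
| 0.6 | 0.175 | same OR | 9.8% | 80.8 → 84.3% | 2.7 |

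The saving is worth about 0 to 5 patients per arm. For scale, the standard error of the crude difference is √(0.3675/49) = 8.7 points.

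**5. Adding centre.** Further simulations used three centres (Verona and at least two others are planned), 49 per arm and f = 0.375, which implies lo = 0.31. TP risk was either flat or proportional to the PA risk.

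| Analysis | TP flat, crude → adjusted | TP proportional, crude → adjusted |
|---|---|---|
| Main effects: arm, FRS, centre (linear risk difference, robust SE) | 81.0 → 81.6% | 81.3 → 82.4% |
| Mantel-Haenszel on crossed FRS × centre strata | 81.0 → 79.7% | 81.3 → 80.8% |

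With six equal centres (assumed), the crossed Mantel-Haenszel test falls further: 80.8 → 76.9% with TP flat, and 81.0 → 78.9% with TP proportional.

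**6. If centres differ in risk** (spread assumed, not in the documents). The main-effects model gave 83.7% power against 81.8% crude, with type I error about 5% against 4.4% for the crude test. In a separate check, centres of 25/12/12 per arm with PA risks of 40/25/55% gave a crude type I error of 4.5%, against 4.9% stratified. With 40/15/65% these were 3.6% and 5.1%.

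**The case against.** The strongest reply is that nothing is wrong. The chi-square is valid under randomisation and matches the two-proportion test behind the sample size. Chance imbalance is already inside the 8.7-point standard error and the 5% error rate; it is not bias. All of this stands, and it rules out reading the plan as biased or invalid.

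A reader might also infer that FRS strongly predicts the primary endpoint here, taking 31% and 55% as the rates below and at FRS 9-10. The documents do not support that:

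- 31% is the rate for the whole high-risk PD group, not for a lower stratum.
- FRS is a fistula score, and no TP rate by FRS is given.
- Eligibility fixes texture at soft and caps the duct at 3 mm, which restricts two of the four components.
- The sample size section says that no direct data on major morbidity exist for this subset.

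A shift of 0.24 × 0.098 = 2.3 points per SD would follow only if the same 24-point gradient held in both arms. At that share (f = 0.375), the shift is 0.12 × 0.098 = 1.2 points with TP flat and 0.165 × 0.098 = 1.6 with TP proportional. A gain from 81% to 86% needs rates of 20% and 73%, which conflicts with the documented 55%.

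Finally, adjustment is not free in every form: stratifying on crossed FRS × centre cells can lose power. That stands against crossed strata. It does not reach a main-effects model, which lost no power in the scenarios checked.

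**Conclusion.** The point holds as a modest missed efficiency. The primary analysis uses neither the centre-wise lists nor a score that is calculated before allocation. Under rates anchored to the documents, main-effects adjustment is worth roughly 0 to +3 points of power at 49 per arm. A one-SD FRS imbalance moves the crude difference by about 1 to 2 points over the middle of the assumed range (0.5 to 2.7 at its ends), against a 25-point target. If centres differ in risk, the crude test is slightly conservative.

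These sizes rest on an assumed FRS 9-10 share, an assumed FRS effect after TP, assumed centre structure and no dropout. The simulations used FRS as two levels and a linear risk-difference model; a continuous score or a logistic model was not simulated. The result does not make the planned test wrong, and it is no ground for changing the sample size.

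**What to change.** In the Statistical Analysis section, pre-specify the primary analysis as a model with main effects for arm, FRS (continuous) and centre. Report the standardised risk difference with a 95% CI. State a rule for pooling small centres. Specify that the FRS entered is the value recorded before allocation, because blood loss is one of its components and continues to accrue after allocation. Keep the crude chi-square as a sensitivity analysis and keep 49 per group. Do not use Mantel-Haenszel on fully crossed FRS × centre strata: sparse cells can cost about 1 point of power or more.

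The cost is a few lines of text, the pooling rule and slightly more analysis work. No new data are needed.
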